4.6.3. Ranked Secondary Efficacy Endpoints

All secondary efficacy endpoints will be summarized by descriptive statistics for each treatment group, for each time point, including summaries of change from baseline when applicable. As with the primary analysis, individual linzagolix versus placebo treatment groups comparisons will be made.

Sponsor:	ObsEva		
Protocol:	18-OBE2109-003		
Document Version No.:	V5.0 Document Date: 13-JUN-2022		

In general, between-group comparisons for continuous endpoints will be analyzed via analysis of (co)variance. Between-group comparisons for binary endpoints will be analyzed via logistic regression. Between-group comparisons for ordinal categorical data will be analyzed using a Mantel-Haenszel test or using Koch's method when there is also a baseline covariate.

As described in section 4.2.5, the ranked secondary endpoints will follow a fixed-sequence testing strategy within the group, so as to maintain the family-wise type I error rate.

For endpoints based on daily ediary data, analyses will use observed data only in such cases, provided that a minimum number of 43% (at least 12 days of each 28-day period) completed daily eDiary entries are available. Subjects who have less than the minimum number of days available will be excluded from the analysis. This is valid under the assumption that such data is MAR, conditional on the baseline value.

4.6.3.1. Change from baseline to Month 6 in DYS (VRS) and in NMPP (VRS)

Mean pelvic pain scores for DYS and for NMPP for each subject will be calculated in the same way as for the primary endpoints. The change from baseline to Month 6 (the last 28 days of randomized treatment up to the Month 6 visit, defined as the last 28 days prior to and including the last treatment administration date as defined in Section 4.2.11, or the 28 calendar days immediately prior to and including the last dose date for subjects who discontinue treatment prior to Month 6) in DYS using the VRS, and the change from baseline to Month 6 (the last 28 days of randomized treatment up to the Month 6 visit, defined as the last 28 days of randomized treatment up to the Month 6 visit, defined as the last 28 days prior to and including last treatment administration date as defined in Section 4.2.11 or the 28 calendar days immediately prior to and including the last dose date for subjects who discontinue treatment administration date as defined in Section 4.2.11 or the 28 calendar days immediately prior to and including the last dose date for subjects who discontinue treatment prior to Month 6) in NMPP using the VRS, will be analyzed via analysis of covariance with treatment group as the main effect (three values) and including the baseline pain score as a covariate. The mean pelvic pain scores for DYS and NMPP and change from baseline will also be descriptively summarized.

SAS Code (may be updated at analysis stage to fit the data): Analysis of covariance

```
proc GLM data=dataset order=internal ;
    class treatment;
    model chg = base_pain treatment;
    lsmeans treatment / pdiff = control('1') cl alpha=0.05 at means
adjust=bon;
    ods output lsmeans = lsm diff=pvals lsmeancl=lsmeancl
lsmeandiffcl=lsmeandiffcl; * contains the adjusted means;
```

run;

CRS-BS-TP-000005 V 1.0

Page 66 of 127

Cytel Confidential: This is a controlled document and shall not be changed, saved, copied or reproduced by any unauthorized person.

Sponsor:	ObsEva		
Protocol:	18-OBE2109-003		
Document Version No.:	V5.0	Document Date:	13-JUN-2022

The number and percentage of subjects with a reduction of X from baseline to Month 6 for DYS, with a reduction of X from baseline to Month 6 for NMPP will be presented. The reduction will be defined in a similar way as for the primary endpoint, but for the Month 6 timepoint. The value for the threshold X will be obtained from the MCT analysis based on blinded Month 6 data (X can be different for DYS and NMPP).

4.6.3.2. Change from baseline to Month 6 in dyschezia (Numeric Rating Scale - NRS)

Mean dyschezia scores for each subject will be calculated by averaging over the corresponding 28 calendar days immediately prior to and including the day of the last treatment administration as defined in Section 4.2.11 (or the 28 calendar days immediately prior to and including the last dose date for subjects who discontinue treatment prior to Month 6). The baseline mean dyschezia score will be calculated by averaging scores over the two baseline menstrual cycles. The change from baseline to Month 6 in dyschezia using the NRS will be analyzed via analysis of covariance with treatment group as the main effect (three values) and including the baseline pain score as a covariate. The mean dyschezia score and change from baseline will be descriptively summarized as well.

The number and percentage of subjects with a reduction of X from baseline to Month 6 for dyschezia will be presented. The reduction will be defined in a similar way as for the primary endpoint, but using dyschezia scores at the Month 6 timepoint. The value for the threshold X will be obtained from the MCT analysis based on blinded Month 6 data.

4.6.3.3. Change from baseline to Month 6 in overall pelvic pain (NRS)

The change from baseline to Month 6 (the last 28 days of randomized treatment up to the Month 6 visit, defined as the last 28 days prior to and including last treatment administration date as defined in Section 4.2.11 or the 28 calendar days immediately prior to and including the last dose date for subjects who discontinue treatment prior to Month 6) in overall pelvic pain using the NRS will be analyzed the same way as for dyschezia as described in Section 4.6.3.2. The baseline will be computed as the mean of the overall pelvic pain score over the two baseline menstrual cycles.

The number and percentage of subjects with a reduction of X from baseline to Month 6 for Overall Pelvic Pain will be presented. The reduction will be defined in a similar way as for the primary endpoint, but for Overall Pelvic Pain score at the Month 6 timepoint. The value for the threshold X will be obtained from the MCT analysis based on blinded Month 6 data.

4.6.3.4. Change from baseline to Month 6 in the interference of pain with the ability to perform daily activities, measured using the pain dimension of the Endometriosis Health Profile-30 (EHP-30)

The EHP-30 pain dimension consists of 11 items each addressing the effect of pain on various activities and each assessed on a 5-point scale (0=Never through to 4=Always). The EHP-30 Pain Impact Domain comprises the following items:

Sponsor:	ObsEva		
Protocol:	18-OBE2109-003		
Document Version No.:	V5.0	Document Date:	13-JUN-2022

During the last 4 weeks, because of your endometriosis, how often have you...

- 1. Been unable to go to social events because of the pain?
- 2. Been unable to do jobs around the house because of the pain?
- 3. Found it difficult to stand because of the pain?
- 4. Found it difficult to sit because of the pain?
- 5. Found it difficult to walk because of the pain?
- 6. Found it difficult to exercise or do the leisure activities you would like to do because of the pain?
- 7. Lost your appetite and/or been unable to eat because of the pain?
- 8. Been unable to sleep properly because of the pain?
- 9. Had to go to bed/lie down because of the pain?
- 10. Been unable to do the things you want because of the pain?
- 11. Felt unable to cope with the pain?

This endpoint shall be scored as per the Appendix B in Section 7.2, resulting in a score on a scale from 0 (best possible health status) to 100 (worst possible health status). The score will be computed as the sum of raw scores of each item (ranging from 0 to 4) divided by the maximum possible raw score (11*4), multiplied by 100. The change from baseline to Month 6 (the last 28 days of randomized treatment up to the Month 6 visit) in ability to perform daily activities, measured using the pain dimension of the EHP-30 will be analyzed via analysis of covariance with treatment group as the main effect (three values) and including the baseline value as a covariate. EHP-30 score at baseline and Month 6 and change from baseline will also be descriptively summarized.

The number and percentage of subjects with a reduction of X from baseline to Month 6 for the EHP-30 Pain Dimension score will be presented. The value for the threshold X will be obtained from the MCT analysis based on blinded Month 6 data.

4.6.3.5. Change from baseline to Month 6 in dyspareunia (VRS)

Responses to the daily dyspareunia questions will be scored as follows. Responses on days where the subject was not sexually active for reasons other than their endometriosis will not be included in the analysis.

Response	Score
No pain during sexual intercourse.	0

CRS-BS-TP-000005 V 1.0

Page 68 of 127

Cytel Confidential: This is a controlled document and shall not be changed, saved, copied or reproduced by any unauthorized

Cytel

Statistical Analysis Plan

Sponsor:	ObsEva		
Protocol:	18-OBE2109-003		
Document Version No.:	V5.0	Document Date:	13-JUN-2022

I was able to tolerate the pain during sexual intercourse.	1
Intercourse was interrupted due to pain.	2
I avoided sexual intercourse because of anticipation of pain.	3

Mean dyspareunia scores for each subject will be calculated by averaging over the corresponding days during the 28 calendar days immediately prior to and including the last treatment administration date as defined in Section 4.2.11 (or the 28 calendar days immediately prior to and including the last dose date for subjects who discontinue treatment prior to Month 6). The baseline mean dyspareunia score will be calculated by averaging scores over the two baseline menstrual cycles.

Dyspareunia scores will be summarized using the FAS and for the subgroup of subjects who have a mean dyspareunia score > 1 at baseline. The statistical analysis of dyspareunia will only use the sub-group of subjects in order to estimate the effect of treatment on such subjects. It is anticipated that this will be around 60% to 70% of the randomized subjects. This is a baseline assessment and does not influence the blinded, randomized treatment group. As per section 4.2.5, the type I error is maintained due to using fixed-sequence testing strategy. The change from baseline to Month 6 in dyspareunia will be analyzed via analysis of covariance with treatment group as the main effect (three values) and including the baseline value as a covariate.

The number and percentage of subjects with a reduction of X from baseline to Month 6 for Dyspareunia will be presented. The reduction will be defined in a similar way as for the primary endpoint, but for Dyspareunia score and for the Month 6. The value for the threshold X will be obtained from the MCT analysis based on blinded Month 6 data.

4.6.3.6. No analgesic use / no opiate use for EAP during the preceding 4-week period at Month 6

The analysis of the proportion of subjects reporting no analgesic use for EAP, and the proportion of subjects reporting no opiate use for EAP during the preceding 4-week period at Month 6 (last 28 days prior to and including last treatment administration date) will be conducted using a logistic regression model, with treatment group as the main effect (three values).

In addition to analgesic use for EAP as collected in the eDiary, concomitant medications in the study will be reviewed and medications to be considered as analgesic use for endometriosis associated pain will be confirmed by the Sponsor and be provided in an excel file prior to Database Lock. They may include any

Sponsor:	ObsEva		
Protocol:	18-OBE2109-003		
Document Version No.:	V5.0	Document Date:	13-JUN-2022

medication with the ATC codes from WHO drug dictionary version March 2016 as listed in Table 6 in Section 4.6.2.2.

In addition to analyzing the absence of analgesic use for EAP, the amount used for each 4-week period up to Month 6 will be summarized as a continuous variable, including the change from baseline. This analysis will be based on e-diary data only, as subjects did not record opioid intake in the concomitant medication page on a tablet-by-tablet basis.

As it is likely that more than one opioid will be used (opioid analgesic may be different depending on countries), the amount of opioid used will be converted to morphine milligram equivalents (MME) in order to better quantify the actual amount of opioids used by subjects.

For countries (Spain, Hungary, France, Czech Republic) where several opioids with different MME were allowed, the data collected in the e-diary is not sufficient to determine exactly which opioid was used and what the MME is. The MME will be derived as the average of possible MME of the allowed opioids in the country.

No opioids are allowed in Ukraine. Subjects from Ukraine will therefore be excluded from the summary in MME. If some opioids are nevertheless recorded for subjects from Ukraine, they will not be considered for the summary in MME, as the conversion in MME would be unknown. Those opioids records will however be considered for other analgesic use analyses not requiring conversion in MME.

The baseline amount of analgesic used will be computed by averaging the amount used during the two baseline menstrual cycles.

Conversion to MME by country is described in Table 7.

Country	Permitted rescue analgesic: Narcotic analgesic local equivalent	Conversion in morphine milligran equivalents
Austria	tramadol 37.5mg + paracetamol 325mg	3.75 MME
Bulgaria	tramadol 37.5mg + paracetamol 325mg	3.75 MME
Czech Republic	codeine 30mg	4.125 MME

Table 7 Morphine Milligram Equivalents for Narcotic Analgesics

Sponsor:	ObsEva		
Protocol:	18-OBE2109-003		
Document Version No.:	V5.0	Document Date:	13-JUN-2022

	paracetamol 500 mg+ codeine 30 mg tramadol 37.5mg + paracetamol 325mg	
France	paracetamol 500 mg+ codeine 30 mg tramadol 37.5mg + paracetamol 325mg	4.125 MME
Hungary	paracetamol 500 mg+ codeine 30 mg codeine 30mg tramadol 37.5mg + paracetamol 325mg	4.125 MME
Poland	tramadol 37.5mg + paracetamol 325mg	3.75 MME
Romania	codeine 30mg paracetamol 500 mg+ codeine 30 mg	4.5 MME
Spain	paracetamol 500 mg+ codeine 30 mg tramadol 37.5mg + paracetamol 325mg	4.125 MME
Ukraine	No Narcotic Analgesic allowed	
US	5 mg hydrocodone + 300 mg acetaminophen	5 MME

Sponsor:	ObsEva		
Protocol:	18-OBE2109-003		
Document Version No.:	V5.0	Document Date:	13-JUN-2022

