13.5.3.5 Change from baseline to Month 6 in dyspareunia (VRS)

The responses to the daily dyspareunia questions will be scored as follows. Responses where the subject was not sexually active for reasons other than their endometriosis will not be included in the analysis.

Response	Score
No pain during sexual intercourse.	0
I was able to tolerate the pain during sexual intercourse.	1
Intercourse was interrupted due to pain.	2
I avoided sexual intercourse because of anticipation of pain.	3

Mean dyspareunia scores for each subject will be calculated by averaging over the corresponding 28 calendar days immediately prior to and including the day of the Month 6 visit (or the 28 calendar days immediately prior to and including the last dose date for subjects who discontinue treatment prior to Month 6). The baseline mean dyspareunia score will be calculated by averaging over the two complete menstrual cycles during screening.

Dyspareunia scores will be summarized using the FAS and for the sub-group of subjects who have a mean dyspareunia score > 1 at baseline. The statistical analysis of dyspareunia will only use the sub-group of subjects in order to estimate the effect of treatment on such subjects. It is anticipated that this will be around 60% to 70% of the randomized subjects. This is a baseline assessment and does not influence the blinded, randomized treatment group. As per section 13.1, the type I error is maintained due to using fixed-sequence testing strategy. The change from baseline to Month 6 in dyspareunia will be analyzed via analysis of co-variance with treatment group as the main effect (three values) and including the baseline pain score as a covariate.

13.5.3.6 No analgesics use / no opiate use for EAP during the preceding 4-week period at 6 months

The analysis of the proportion of subjects reporting no analgesic use for EAP, and the proportion of subjects reporting no opiate use for EAP, during the preceding 4-week period at 6 months will be conducted using a logistic regression model, with treatment group as the main effect (three values).

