4. STATISTICAL METHODS

4.1. Sample Size Justification

The planned sample size for this study is 150 subjects per treatment group (450 subjects in total).

An overall two-sided type I error of 0.05 will be used. As there are two linzagolix versus placebo comparisons, Bonferroni corrected p-values will be produced (raw p-values will be multiplied by two prior to comparing to 0.05). The planned sample size considers the hierarchical, fixed sequence testing of the ranked secondary endpoints as well as the co-primary endpoints. The assumptions used for the sample size calculations are based on analyses of clinically meaningful reduction in pain with a stable or decreased use of analgesics from the Phase 2b Edelweiss study. Calculations were performed using East[®] 6.5 software.

One hundred and fifty (150) subjects per treatment group will provide a power greater than 95% to reject the null hypothesis for both co-primary endpoints for either treatment group, assuming a placebo response rate of 14.6% and an active treatment response rate of 48.6% (75 mg, Edelweiss Phase II study results) or 64.7% (200 mg, Edelweiss Phase II study result) for DYS, and a placebo response rate of 18.8% and an active treatment response rate of 42.1% (75 mg, Edelweiss Phase II study result; the response rate for 200 mg in Edelweiss was lower but was inconsistent with the other doses and other timepoints for the same dose and so was not used) for NMPP. In addition, 150 subjects per treatment group provides 85% power to reject the null hypotheses for all the ranked secondary endpoints based on the observed results from the placebo and 200 mg treatment group in the Edelweiss study.

The values used for the sample size calculations assume that these responses rates are what would be seen on average when under treatment including taking into account any subjects who might withdraw from treatment early; therefore the calculations do not need to be further adjusted for dropouts.

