4.5.2. Baseline Disease Characteristics

The definition of the two baseline menstrual cycles is described in section 4.2.10

Baseline Dysmenorrhea (DYS) and Non-Menstrual Pelvic Pain (NMPP) will be calculated by averaging over the two baseline menstrual cycles, the e-diary daily answers of Endometriosis Related Pelvic Pain (PP VRS Questionnaire). Responses of "None," "Mild," "Moderate," and "Severe" will be assigned a score of 0, 1, 2, and 3, respectively. Dysmenorrhea will be computed using days with uterine bleeding, defined as those days on which the subject records any uterine bleeding or spotting in the subject eDiary; Non-Menstrual Pelvic Pain will use days with no uterine bleeding.

The baseline analgesic use will be calculated as the mean of daily pill count of analgesics over the two baseline menstrual cycles for each class of rescue analgesics (endometriosis-associated: Ibuprofen, Narcotic Analgesic) collected in the eDiary, separately for bleeding days, non-bleeding days and overall.

Dysmenorrhea, Non-Menstrual Pelvic Pain and Analgesic use will be summarized as continuous variables

The average duration of the two baseline menstrual cycles (days) will be summarized. The duration (days) of each of the two individual eligible baseline menstrual cycle will be calculated using the (menstrual start dates provided in the excel file. The duration is computed as (start date of $Cycle_{x+1}$ – start date of $cycle_x$).

The average number of days with uterine bleeding over the two baseline menstrual cycles will be summarized as continuous variables.

The number and percentage of subjects with Normal, Abnormal, Abnormal clinically significant (or Not Assessable) results for Physical Examination, Gynecological Examination, Breast Examination, Mammography, Endometrial Biopsy and PAP Smear assessments will be presented by treatment group and overall. Abnormality details will be provided in data listings.

Transvaginal ultrasound data (i.e., presence of ovarian endometrioma with a diameter of 7 cm or greater, uterus length, width, and depth in mm and corresponding calculated uterine volume in cm3 (using the prolate ellipsoid formula [L x H x W x 0.523]), endometrium thickness in mm, and presence of any uterus, left ovary or right ovary abnormality) will be summarized.

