4.6.2.1.2. Primary Efficacy Analysis

The primary efficacy analysis will be conducted using the FAS.

The analysis of each co-primary endpoint will be conducted using a logistic regression model, with treatment group as the main effect (three values) and including the baseline pain score as a covariate. Individual linzagolix versus placebo treatment group comparisons will be made using the same logistic regression model. Estimated odds-ratios and 97.5% intervals of proportions of responders of linzagolix treatment groups versus placebo will be presented, along with Bonferroni corrected p-values. Estimates of proportions of responders with 95% confidence intervals will be presented as well, estimated at the overall mean baseline pain score.

SAS Code (may be updated at analysis stage to fit the data):

```
PROC LOGISTIC data=dataset order=internal;
Class treatment(ref=placebo) / param=glm ;
Model resp(event= "Yes")= treatment base_pain /alpha=0.05;
Oddsratio treatment ;
Lsmeans treatment / ilink exp cl alpha=0.05 at means diffs=control('1')
adjust=bon;
Ods output OddsRatiosWald=or ModelANOVA=ma ParameterEstimates=pe
lsmeans=lsm diffs=diffs;
```

Run;

In addition, the mean pelvic pain scores for DYS and NMPP and change from baseline for the last 28 days prior to Month 3 or the last 28 days of treatment (or less) for subjects who discontinued will be summarized as continuous variables by treatment group. Cumulative distribution functions (CDF) for change from baseline at Month 3 for DYS and NMPP will be provided, with separate lines for each treatment group. The x-axis will present the different values for the DYS or NMPP change from baseline, and the y-axis will present the proportion of subjects reaching each value of change. Vertical lines of the relevant MCT thresholds obtained at the Month 3 responder threshold analysis will be displayed on the plots.

The number and percentage of subjects with:

- Reduction of X for DYS,
- Reduction of X for NMPP,

Sponsor:	ObsEva		
Protocol:	18-OBE2109-003		
Document Version No.:	V5.0 Document Date: 13-JUN-2022		

- Stable or decreased use of analgesics for EAP during bleeding days, during non-bleeding days, and overall,
- Reduction of X for DYS and stable or decreased use of analgesics for EAP (during bleeding days),
- Reduction of X for NMPP and stable or decreased use of analgesics for EAP (during non-bleeding days),

will be presented.

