4.6.4.5. Change from baseline to each scheduled assessment in mean daily dyspareunia scores

Sponsor:	ObsEva		
Protocol:	18-OBE2109-003		
Document Version No.:	V5.0	Document Date:	13-JUN-2022

reported during the previous 4-week period on the dyspareunia VRS

The actual value and change from baseline in mean daily dyspareunia scores will be summarized as a continuous variable for each 28-day period. An analysis of covariance will be performed for each period.

Subjects not sexually active for reasons other than endometriosis will have missing values for the corresponding 4-week periods. Subjects not sexually active for reasons other than endometriosis at baseline will be excluded from the analysis.

4.6.4.6. Change from baseline to each scheduled assessment in mean daily dyschezia scores reported during the previous 4-week period assessed on the dyschezia NRS

The actual value and change from baseline in mean daily dyschezia scores will be summarized as a continuous variable for each 28-day period. An analysis of covariance will be performed for each period.

4.6.4.7. Change from baseline to each scheduled assessment in non-opioid, opioid and combined analgesic use for EAP during the previous 4-week period based on pill count in the eDiary

Non-opioid, opioid and combined analgesic use for EAP will be measured using the mean of daily pill count collected in the eDiary over each 28-day period. For non-opioid and combined analgesic use, descriptive summary (actual values and changes from baseline) and analysis of covariance for each period will be performed. Due to a low number of subjects using any opioids, opioids use will not be analyzed as a continuous variable, only a listing with by subject opioid use mean daily pill count will be provided.

The number and percentage of subjects reporting no analgesic use for EAP, and the proportion of subjects reporting no opiate use for EAP at baseline and during the preceding 4-week period at Month 3 (last 28 days prior to and including last treatment administration date) will be presented. The proportion of subjects with no analgesic use for EAP, and with no opiate use for EAP will be conducted using a logistic regression model, with treatment group as the main effect. For these proportions, in addition to eDiary analgesic use, data from the concomitant medication page will be used, as described in Section 4.6.3.6.

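### Endpoint 7 is tested without its available baseline, and Ukrainian opioid entries that the SAP calls entry errors still count for endpoint 8 and the co-primary analgesic rule: power is lost, validity is not

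*SAP*

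**What the plan says.** **Models.** For the co-primaries, SAP 4.6.2.1.2 specifies logistic regression "with treatment group as the main effect (three values) and including the baseline pain score as a covariate". Ranked endpoints 1 to 6 use analysis of covariance with the baseline value; for example, dyspareunia (SAP 4.6.3.5) is "analyzed via analysis of covariance with treatment group as the main effect (three values) and including the baseline value as a covariate". For the proportions with no analgesic use and no opiate use, SAP 4.6.3.6 stops at treatment group: the analysis "will be conducted using a logistic regression model, with treatment group as the main effect (three values"). Protocol 13.5.3.6 does the same: "conducted using a logistic regression model, with treatment group as the main effect (three values").

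**Baseline.** SAP 4.5.2 already derives baseline analgesic use, "calculated as the mean of daily pill count of analgesics over the two baseline menstrual cycles for each class of rescue analgesics".

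**Power.** SAP 4.1 states that "150 subjects per treatment group provides 85% power to reject the null hypotheses for all the ranked secondary endpoints", based on the placebo and 200 mg results of the Phase 2b study. The rates behind that figure are not given.

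**Ukraine.** Protocol 10.6.1 and SAP Table 7 permit no narcotic analgesic there. SAP 4.6.3.6 and 4.6.4.8 leave Ukrainian opioid records out of the morphine milligram equivalent (MME) work, because no conversion is known, and keep them in every analgesic analysis that needs no conversion. The V3.0 entry in SAP section 5, which gives the reason for this current rule, attributes the records to an eDiary entry problem that had been confirmed.

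**Sparsity.** SAP 4.6.4.7 says: "Due to a low number of subjects using any opioids, opioids use will not be analyzed as a continuous variable".

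**The concern.** Both endpoints are in the fixed confirmatory sequence. If endpoint 7 fails for a dose, endpoint 8 cannot be claimed for that dose; if endpoint 8 fails, nothing further is blocked. Analgesic use before treatment is a natural predictor of analgesic use at Month 6, so leaving it out of the endpoint 7 model gives up power for no evident reason.

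The Ukrainian rule looks inconsistent with its own justification. If the records are known entry errors, the lack of an MME conversion explains why they leave one analysis but not why they stay in the others. Endpoint 8 is defined in the same section and needs no conversion, so they count there. The co-primary analgesic rule (SAP 4.6.2.1.1 and Appendix A) uses diary pill counts by class with no exception for Ukraine, so they count there too.

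**Working it through.** **1. The plan's own figure.** Inputs from SAP 4.1: 150 per arm, two-sided 0.025 per comparison, NMPP response 18.8% versus 42.1%. Pooled normal approximation:

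power = Φ{ [ |p1 − p0|√n − z√(2p̄(1 − p̄)) ] / √( p0(1 − p0) + p1(1 − p1) ) }, with z = 2.241

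= Φ[(2.854 − 1.459)/0.630] = Φ(2.216) = 98.7%.

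Dysmenorrhea is above 99.9% at either dose, so the stated co-primary power of more than 95% reproduces. The 85% for the ranked endpoints cannot be reproduced. It is a joint power, so endpoint 7 alone must have at least 85% for 200 mg versus placebo; only scenarios meeting that are used below.

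**2. Endpoint 7: gain from a baseline covariate.** Rates and covariate strength are assumptions. Method: 8,000 simulated trials per scenario, three arms of 150 (75 mg rate midway), standard normal covariate, marginal rates held fixed, Wald test of 200 mg versus placebo at 0.025. Gain in percentage points by baseline effect (log-odds per SD):

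| No analgesic use, placebo vs 200 mg | Unadjusted power | 0.3 | 0.5 | 0.7 | 1.0 | 1.5 |
|---|---|---|---|---|---|---|
| 20% vs 37.5% | about 87% | 0.6 | 1.4 | 2.6 | 5.5 | 8.5 |
| 20% vs 39% | about 92% | 0.3 | 0.9 | 1.7 | 4.2 | 5.7 |
| 35% vs 54% | about 86% | 0.7 | 2.6 | 4.3 | 6.0 | 9.9 |

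A separate simulation with a yes/no baseline covariate (25% versus 43%, baseline odds ratio 3 to 12) gave gains of about 1 to 8 points. With no treatment effect, rejection was 2.2% to 2.8% for both the adjusted and unadjusted models, against a nominal 2.5%.

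**3. Does anything remove the Ukrainian records?** The diary cleaning rules (SAP 4.2.8.3) and mapping tables (Appendix E) do not mention them. The Ukraine sensitivity analyses (SAP 4.6.4.1 and 4.8.3) cover only follow-up data after 24 February 2022. The Per Protocol list (SAP 3.2) has unauthorised therapy as a possible exclusion but does not address false entries.

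**4. What one record does.** For endpoint 8, a single entry in the 28 days makes the subject a user and moves that arm's rate by 1/150 = 0.67 points. Under Appendix A:

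- On treatment, narcotic entries can give *Increase* in a subject with none at baseline, beyond the allowance of one extra pill a month, or in a subject with some, if the rise exceeds 15%.
- At baseline, a false entry can give *Stable/Decrease*: a subject with no true baseline use who starts ibuprofen would read as having replaced a narcotic with ibuprofen.

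**5. Size for the co-primary.** If false entries turned 5% of each arm's responders into non-responders, NMPP becomes 18.8% × 0.95 = 17.9% versus 42.1% × 0.95 = 40.0%. Power falls from 98.7% to 98.0%, a loss of 0.7 points. Dysmenorrhea shows no visible change.

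**6. Size for endpoint 8, illustration only.** With true user rate q and false-entry share f in both arms, the recorded rate is 1 − (1 − q)(1 − f). Exact binomial enumeration, Wald test, power by f:

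| Opiate use, placebo vs active | Expected users in the two arms | f = 0 | 1% | 2% | 4% |
|---|---|---|---|---|---|
| 25% vs 10% | 52.5 | 89% | 87% | 85% | 80% |
| 15.5% vs 4% | 29.25 | 88% | 84% | 80% | 72% |
| 8% vs 2% | 15 | 42% | 40% | 36% | 28% |
| 6% vs 2% | 12 | 15% | 16% | 16% | 13% |

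The first two rows imply more users than the SAP's remark about low opioid use suggests. The last two show that with very few users power is poor with or without the errors. The documents give neither the user rates, nor Ukrainian enrolment, nor the number of records.

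**The case against.** The covariate point is an efficiency preference. The unadjusted test is valid, the protocol and SAP agree on it, and logistic regression is the SAP's general rule for binary endpoints. The gains tabulated are also favourable: they assume a normal covariate that acts linearly. With a skewed pill count containing zeros, gains at 20% versus 37.5% fell from about 2, 5 and 8 points to about 1, 3 and 5. The diary baseline also omits the reviewed concomitant medications that count towards the endpoint. All of this stands, and it limits the size; the direction does not change.

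On Ukraine, keeping records as entered is an explicit prespecified rule, and the description of them as errors appears only as the reason for a change. The documents do not say whether no drug, ibuprofen or an unpermitted opioid was taken. That is a fair reason to list and classify the records before setting any aside. It is not a reason to count entries already confirmed as wrong.

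Four stronger readings might be inferred, and the documents support none of them:

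- *The Ukrainian records bias the comparison or inflate type I error.* Misclassification can go either way for a subject, but under blinding the errors should not differ by arm.
- *The co-primary result is at real risk.* The check above gives under 1 point of power, and the one-pill allowance limits the effect further.
- *The stated 85% is wrong.* Its inputs are not given, so this cannot be shown.
- *Endpoint 8 also needs a baseline covariate.* With so few opioid users, adding a covariate raises sparse-data problems and its gain cannot be sized.

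**Conclusion.** Both parts hold, with modest consequences. Omitting baseline from endpoint 7 costs about 1 to 9 points of power at 20% versus 37.5% (0.3 to 9.9 over the three scenarios), and less with a skewed pill count. Rates and covariate strength are assumed throughout.

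Retaining the Ukrainian records contradicts the SAP's own account of them. It dilutes endpoint 8 by an amount that cannot be sized from the documents, and it is expected to cost the co-primaries under 1 point, if up to 5% of responders are affected. For the co-primaries the issue is correct classification of subjects rather than lost power. That type I error is unaffected rests on false entries being equally frequent in each arm, which a count by arm would check.

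**What to change.** **Ukrainian records.** List the confirmed entry errors blind to treatment. Do not count them as opioid use, at baseline or on treatment, in SAP 4.6.3.6, 4.6.4.7 and Appendix A, and state for each whether it still counts as analgesic use for endpoint 7. Report affected subjects by arm, with the as-recorded analysis alongside.

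**Endpoint 7.** Add diary baseline mean daily analgesic pill count to the no-analgesic model in SAP 4.6.3.6. Leave the endpoint 8 model as it is.

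**Timing.** SAP 4.3 allows unblinded results to reach the sponsor once the Month 6 thresholds are in the SAP. V4.0 added them and V5.0 (13 June 2022) came later, so release may already have happened; the documents give no date. A change to a confirmatory test is credible only if dated before release. If results by arm have been released, keep the ranked and co-primary tests as written and report both changes as labelled sensitivity analyses.

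**Cost.** SAP wording, one blinded listing and parallel runs; the diary baseline already exists. The adjusted odds ratio for endpoint 7 would be conditional on baseline use.
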